3.2.1 Statin titration

Statin medications will be titrated over the initial 6 months of the study to reach protocol defined LDL cholesterol targets. Should a participant's LDL fluctuate after the 6 month visit, bringing them outside of their target range, statin dosage may be increased or decreased as necessary to return them to their protocol assigned target. Participants who have not reached their LDL target after the 6 month dose adjustment will be removed from study treatment as per off-treatment criterion 3, below. (3.4.1)

3.2.2 Response to abnormal results

All clinically abnormal test results will be relayed to participants' primary care physician(s) or other designated third party. Participants will be instructed to consult with their physician for follow up and referral to specialists as appropriate.

In addition, abnormal laboratory values potentially due to statin treatment (ALT, AST, alkaline phosphatase, CK > 1000 U/L) that are asymptomatic and less than 3 times the upper limit of normal as specified by the NIH Clinical Center clinical laboratory will be repeated within 2 weeks of the initial result. If results are stable or improved, further testing will occur at normally scheduled study intervals. Should results worsen, increases in statin dosage that immediately preceded the abnormal result will be reversed and laboratory results repeated in 2 weeks. ALT, AST, alkaline phosphatase reaching more than 3 times the upper limit of normal or CK >1000 U/L will be considered a serious adverse event as per section 8.1

3.3 Concurrent Therapies

N/A

3.4 Criteria for removal from Treatment/Protocol

3.4.1 Off Treatment Criteria:

Subjects who come off treatment will be returned to usual care for cardiac risk factors as directed by their primary physician. If they consent to continue imaging follow up, they will complete imaging as per protocol and be analyzed according to their original treatment group assignment.

- 1. Occurrence of a clinical cardiovascular event including myocardial infarction, acute coronary syndrome, angina, heart failure, stroke or revascularization.
- 2. Inability to continue on study medications (adverse reaction, not wanting to adhere to the study medications)
- 3. Inability to reach our study LDL target after 6 months of titration (study visit 4)
- 4. Elevations of liver enzymes three times the upper limits of normal or any elevation accompanied by symptoms compatible with hepatitis, i.e.: fatigue, sluggishness, anorexia and weight loss.
- 5. Myopathy defined as muscle pain with serum creatinine kinase concentrations > 1000 U/L.

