1.0 Introduction

1.1 Study Objectives:

The purpose of this study is to evaluate the hypothesis that use of atherosclerosis imaging to set targets for cholesterol lowering therapy will result in greater regression of atherosclerosis than standard therapy.

The primary efficacy endpoint of this study is the wall volume of the internal carotid arteries as measured by magnetic resonance imaging.

Secondary endpoints are

- A. Arterial stenosis and plaque volume measured by coronary MDCTA
- B. Dosage of statin medications required to achieve LDL targets.
- C. Combined incidence of stroke, nonfatal MI, myocardial revascularization, hospitalization for unstable angina or heart failure and death.
- D. FDG plaque uptake within the carotid and coronary arteries.

E. Reproducibility of arterial stenosis and plaque volume measured by MDCTA.

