traditional risk-factor based care). This hypothesis will be tested in a study in which subjects are entered and then followed until either (a) the terminal event occurs, or (b) they drop out of the study, or (c) the study ends and the patient is censored while still being actively followed. The study design calls for an accrual period of 50 months and a follow-up period of 24 months. Computation of power for this analysis is based on a hazard ratio of 0.50. Specifically, it assumes hazard rates of 1.00 for the standard care group, versus 0.50 for the image guided group. Since the hazard rate is constant across months, this is equivalent to median survival times of 0.69 years for the standard treatment versus 1.39 years for the image guided intervention group.

The power analysis for the secondary outcome (clinical events) was based on the paper by Brown et al.²⁴ This paper reported mortality rates at 30 months in two treatment groups (2/48 = 0.042 and 3/46 = 0.065) and a control (10/52 = 0.192). We used these rates, as well as the combination for the two treatment groups (5/94 = 0.053). The calculation of power was based on the log-rank test⁽²⁵⁾ assuming a 24 month study. Using a twosided test at the 5% level of significance, we obtained the following results.

 			
Treatment	0.042	0.053	0.065
Mortality Rate			
Sample			
Size/group			
50	0.57	0.47	0.38
80	0.82	0.71	0.59
100	0.91	0.82	0.70

Power of the log-rank to detect the indicated difference from control

We assume that the attrition rate will be 0.20 in the 24-month follow-up. Thus, recruiting 200 study participants with 160 anticipated to complete 24 months of follow-up will be sufficient for this study.

Data Analysis:

1. The intent-to-treat and missing data:

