The intent-to-treat (ITT) approach will be used for the primary analysis. According to this generally recommended approach, comparisons are made according to randomized treatment assignment, regardless of any changes in dose, schedule or treatment arm. In an ITT analysis, all randomized study participants are included in their assigned treatment groups, regardless of compliance with the assigned treatment regimen. On the other hand, the weakness of ITT is that it assesses the effect of treatment for subjects known not to have used the treatment enough to have any effect. While conventional ITT will be the method used to analyze and report the primary results, in order to derive valid estimates of treatment effect accounting for compliance with therapy, model-based analytical methods will also be employed, and non-ITT analysis will be performed.

In fact, in the present study, we do not foresee noncompliance as a problem since treatment administration is under the control of the study physician rather than the patient. Dropout, however, is always a potential problem. In this study we have assumed a dropout rate of 20%, since we anticipate a lower dropout rate than the 25% in the previous trial. This is because we are using three scans over two years rather than four over 18 months as in the previous study, and many of the previous dropouts were related to MRI anxiety. Thus we do not anticipate problems with differential dropout. In addition, approximately one-third of the dropouts in the previous study were due to problems with niacin flushing, which again will not be a problem in the present study.

2. Multiple outcome measures:

In this clinical trial, we will evaluate multiple outcome measures: changes in plaque architecture and composition measured by MRI, and time to events, including the incidence of cardiovascular and cerebrovascular outcomes and disease-specific death. The following approaches to evaluate multiple outcome measures will be implemented: (i) defining a primary outcome measure; (ii) correcting for multiple testing, such as Bonferroni adjustment; (iii) with data on major clinical events, adopting a combined endpoint, such as time to first cardiovascular event or death, whichever occurs first.

3. Data Analysis:

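### Section 3.4.1 provides only optional imaging after treatment stops; it should state that clinical-event and vital-status follow-up continues to month 24 whatever the imaging consent

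*Combined protocol and SAP*

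**What the plan says.** Section 3.4.1 (Off Treatment Criteria) first says: "Subjects who come off treatment will be returned to usual care for cardiac risk factors as directed by their primary physician". It continues: "If they consent to continue imaging follow up, they will complete imaging as per protocol"; the same sentence, under the same condition, adds that they will be analysed in the group to which they were first assigned. Five criteria follow. Criterion 1 is "Occurrence of a clinical cardiovascular event including myocardial infarction, acute coronary syndrome, angina, heart failure, stroke or revascularization". Criterion 2 is inability to stay on study medication. Criterion 3 is "Inability to reach our study LDL target after 6 months of titration (study visit 4"). Criteria 4 and 5 concern liver enzymes and myopathy. Coming off study is a separate status, in section 3.4.2.

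Secondary endpoint C in section 1.1 is "Combined incidence of stroke, nonfatal MI, myocardial revascularization, hospitalization for unstable angina or heart failure and death". None of its components needs a scan.

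Section 6.0 follows patients for this endpoint until the event, dropout from the study or study end. It applies intent-to-treat to all randomised participants regardless of compliance, and offers time to first cardiovascular event or death as an example of the combined endpoint.

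**The concern.** Two things in section 3.4.1 do not fit an intent-to-treat time-to-event analysis.

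- The condition on imaging consent governs both halves of the sentence: completing the scans, and being analysed in the original group. Read literally, a patient who stops treatment and declines scans has no stated place in the analysis. Section 6.0 says the opposite.
- Section 3.4.1 names no visit, telephone call or record check for events once treatment has stopped. Intent-to-treat governs how collected data are analysed; it cannot supply a myocardial infarction or stroke that nobody recorded.

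The loss need not be random. Criterion 3 depends on the LDL target. In the imaging arm the target comes from the carotid wall-volume tertile, and in the control arm from NCEP risk category. The rate and type of stops may therefore differ by arm, and the independent-censoring assumption of the log-rank test would be in doubt.

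**Working it through.** **1. Does another section fill the gap?**

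| Place | What it gives | Covers a patient off treatment who declines scans? |
|---|---|---|
| 2.3, item J | Clinical follow-up at 7 visits or on notification | Not tied to treatment or scans, but not expressly extended to this patient |
| Appendix B calendar | Adverse-event review at each visit M0 to M24 | Same. For main-study patients M3, M6 and M18 have no imaging; they consist of dispensing, safety labs, medication and adverse-event review, with research blood at M6 |
| 5.1 | Vital status on a case report form | Deaths only |
| 6.0 | Followed to event, dropout or study end | Does not say whether stopping both treatment and scans counts as dropout |

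None ends event follow-up, and none secures it.

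**2. Who is exposed?** In a time-to-first-event analysis, a criterion 1 stop for myocardial infarction, stroke, revascularization, or hospitalized unstable angina or heart failure is already an endpoint C event, so later events change nothing. Criterion 1 also covers angina and heart failure without requiring hospitalization; these can stop treatment before any endpoint. The exposed group is therefore criteria 2 to 5 plus those cases, among patients who decline scans.

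**3. The plan's own figures.** Section 6.0 assumes 20% attrition: 160 / (1 − 0.20) = 200, which matches "recruiting 200 study participants with 160 anticipated to complete 24 months of follow-up". Its log-rank table uses a control rate of 0.192 and treatment rates of 0.042 / 0.053 / 0.065. It gives power 0.82 / 0.71 / 0.59 at 80 per group and 0.91 / 0.82 / 0.70 at 100. Freedman's formula at 80 per group gives 0.82 / 0.75 / 0.66, so it reproduces the first cell and is 4 to 7 points higher in the others. No single method tried reproduced all nine cells. The differences below matter more than the levels.

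**4. Cost of lost events.** Freedman: power = Φ(√d × (1 − HR)/(1 + HR) − 1.96), with HR = ln(1 − pT)/ln(1 − pC) and d = n(pT + pC).

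For pT = 0.053: HR = 0.0545/0.2132 = 0.255, so (1 − HR)/(1 + HR) = 0.593, and d = 80 × 0.245 = 19.6. Power = Φ(4.427 × 0.593 − 1.96) = Φ(0.67) = 0.75.

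The share of events lost is an assumption, since the plan gives no figure:

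| Share lost | Events (0.053 case) | Power at 0.042 / 0.053 / 0.065 |
|---|---|---|
| 0% | 19.6 | 0.82 / 0.75 / 0.66 |
| 5% | 18.6 | 0.80 / 0.73 / 0.63 |
| 10% | 17.6 | 0.78 / 0.70 / 0.61 |
| 20% | 15.7 | 0.73 / 0.65 / 0.56 |
| 30% | 13.7 | 0.67 / 0.59 / 0.51 |

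Each of the first two tenths lost costs about 4 to 5 points.

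**5. Upper limit on what the fix can recover.** Suppose every one of the 20% dropouts were recovered. With constant hazards, time in units of the 24-month study and dropout spread over follow-up, the dropout hazard is δ = −ln(0.80) = 0.223. The probability of an observed event is λ/(λ + δ) × (1 − e^−(λ + δ)).

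- Control, λ = 0.2132: 0.173 instead of 0.192.
- Treatment at 0.053, λ = 0.0545: 0.048 instead of 0.053.
- At 100 per group, events fall from 24.5 to 22.0, about 10%.

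A Lakatos-type log-rank calculation at 100 per group gives 0.91 / 0.85 / 0.77 without dropout and 0.88 / 0.81 / 0.72 with it. The difference is 3 to 5 points.

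**The case against.** The strongest reply is that silence is not a rule. Off treatment and off study are different statuses, stopping treatment is not listed as a censoring reason, the visit schedule and adverse-event review are not tied to drug or scans, and intent-to-treat keeps everyone. This stands against three stronger readings that a reader might infer.

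- *Event follow-up ends when scans are declined.* No section says so. The supportable statement is that it is not provided for.
- *All composite events after stopping are lost.* Patients who continue imaging are still seen at the remaining 12- and 24-month scans, and most criterion 1 stops already are the first endpoint.
- *The plan's table shows 9 to 11 points of power to be regained (80 against 100 per group).* That comparison treats all 40 dropouts as recoverable and as contributing nothing. Some will leave under section 3.4.2, and a log-rank test keeps the time and events before dropout. The limit is about 3 to 5 points.

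The remark in section 6.0 that "many of the previous dropouts were related to MRI anxiety" also helps less than it seems. MRI anxiety is not an off-treatment criterion; such patients would leave mainly at their own request, under section 3.4.2.

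The reply does not remove the gap. The general provisions are not extended to this patient, and the wording of section 3.4.1 itself conflicts with section 6.0.

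**Conclusion.** The point holds as a gap in the plan and a conflict in wording, for a secondary endpoint. Section 3.4.1 provides only optional imaging after treatment stops and ties analysis in the randomised arm to imaging consent, against the intent-to-treat rule. No section secures nonfatal endpoint C data from a patient who stops and declines scans.

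The size is modest and uncertain. With about 20 events, each 10% lost costs roughly 4 to 5 points of power, and even full recovery of the 20% dropout would gain at most about 3 to 5. These figures rest on the plan's event rates, constant hazards and an assumed loss; the plan does not say how many patients will be exposed. Possible arm-related censoring through criterion 3 is the other reason to act. Its direction and size cannot be told from the documents. This is a cheap improvement that should be made; it does not affect the primary MRI endpoint's power.

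**What to change.** Amend section 3.4.1 to state that:

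1. Endpoint C and vital-status follow-up continues to month 24 for every randomised patient, regardless of treatment status or imaging consent, by telephone or primary-physician records, unless the patient refuses all contact.
2. These events count in the randomised arm, and analysis by original assignment does not depend on consent to imaging.
3. A criterion 1 event that is not an endpoint C event does not end event follow-up.

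The treatment-stopping criteria themselves need no change for this. The cost is a short protocol and consent amendment, a few contacts by existing staff (section 4.0 already foresees telephone and electronic contact) and record confirmation of reported events.

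Section 7.4 says the study has been in data analysis only since January 2017, so new contact may no longer be possible. In that case, use available records where consent allows, and report by arm how many patients who stopped treatment had complete event ascertainment to month 24.

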3.4.2 Off Study Criteria

Request of the patient or the attending physician.

Any other clinical or laboratory abnormality which cannot be confidently excluded as a side effect from study medications will lead to discontinuation of an individual patient from the trial.

Subjects who come off study for any reason will be referred back to their primary physician.

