8.1 Adverse Event Definition

Expected Events not reportable

Bruising or extravasation from the intravenous injection, mild contrast allergies that do not require treatment (e.g. headache, pain at site, warmth, flushing, nausea, less than 5 hives) and additional findings on the MRI that require additional workup outside of the study.

Asymptomatic bradycardia (HR <60 bpm) or hypotension (systolic blood pressure <90 mmHg) following beta blockade or nitrates.

Orthostatic symptoms (excluding syncope) following beta blockade or nitrates that resolve without medical intervention.

Muscle discomfort or myalgias without significant (>3 x ULN) elevations of CK.

Expected Events reportable at time of Continuing Review

ALT, AST or alkaline phosphatase elevations between 2-3 times the upper limit of normal *or* requiring discontinuation of statin therapy. (Elevations >3 times the upper limit of normal will be considered a serious adverse event as per below).

Serious Adverse Event reporting

A Serious adverse event is defined as one of the following (in accordance with FDA 21 CFR312.32 and the NIH intramural guidance for principal investigators on reporting adverse events)

death from any cause,

- life threatening event, i.e., an event that places the subject, in the view of the investigator, at immediate risk of death from the event as it occurred.
- any event that requires or prolongs in-patient hospitalization
- any event that results in persistent or significant disability/incapacity
- any congenital anomaly/birth defect diagnosed in a child of a subject who participated in this study.
- other medically important events that in the opinion of the investigator may jeopardize the subject or may require intervention to prevent ongoing injury.

Unexpected Adverse Events

Unexpected adverse events are those that are not described in the published medical literature, in this protocol, or in the informed consent, as being associated with statin therapy and routine CT or MR scanning. Such events might include concurrent unrelated medical illnesses such as ischemic heart disease, stroke, cancer, pneumonia, and other common illnesses seen in the general population but we will attempt to screen for these illnesses with the history and physical exam.

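### Section 3.4.2 takes patients with any other suspected drug side effect out of the trial without providing for further scans, whereas 3.4.1 keeps those who stop treatment in imaging if they consent

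*Combined protocol and SAP*

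**What the plan says.** The protocol separates leaving treatment from leaving the study.

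- **Off treatment (3.4.1).** Patients return to usual care. "If they consent to continue imaging follow up, they will complete imaging as per protocol", and they are analysed in their randomized group. The listed reasons include "Inability to continue on study medications (adverse reaction, not wanting to adhere to the study medications" (item 2), liver enzymes at three times the upper limit of normal (item 4), and "Myopathy defined as muscle pain with serum creatinine kinase concentrations > 1000 U/L" (item 5).
- **Off study (3.4.2).** Apart from a request by the patient or physician, the ground is any other finding, clinical or laboratory, "which cannot be confidently excluded as a side effect from study medications will lead to discontinuation of an individual patient from the trial". What follows is one sentence: "Subjects who come off study for any reason will be referred back to their primary physician". Neither scans nor event follow-up are mentioned.

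Carotid MRI is done at baseline, 12 and 24 months (1.3 and Appendix B). Section 6.0 makes intent-to-treat the primary analysis, with all randomized participants included, and uses a mixed model. It assumes 20% dropout and does not expect dropout to differ between arms. Section 7.4 records that the study moved to data analysis only in January 2017.

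Two smaller points lie nearby. The 5.3 table lists CK above 1000 U/L under discontinuation with no symptom condition, while 3.4.1 item 5 requires muscle pain. The top-tertile LDL target has a lower bound of 40 mg/dL in 1.3 (treatment paragraph) and 3.1, and no lower bound in 1.3 (study design paragraph) and 3.2.

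**The concern.** Stopping a statin because of a suspected reaction may be right for the patient. It gives no reason to stop measuring the carotid wall. Under 3.4.1 the plan accepts this, and under 3.4.2 it does not. Two patients with suspected drug effects can then be handled in opposite ways, one scanned at 24 months and the other not, depending on which paragraph the investigator applies.

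The missing values arise for a reason that may depend on treatment. The trial is open label and statin intensity can differ between arms, so suspected side effects need not be equally frequent in each. Section 6.0 does not address this. Its grounds for expecting little differential dropout are fewer scans and the absence of niacin flushing, and neither concerns removal for a suspected statin effect. It plans further model-based and non-ITT analyses, but for compliance. It sets no sensitivity analysis for missing outcomes.

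The event endpoint is touched as well. Section 6.0 follows each subject to an event, dropout or study end, so a patient taken off study contributes no later events.

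**Working it through.** **1. Who falls under 3.4.2.** The word 'other' makes it a residual category.

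| Situation | Provision | Imaging afterwards |
|---|---|---|
| Cannot continue because of an adverse reaction | 3.4.1 item 2 | Yes, with consent |
| Liver enzymes at 3 times the upper limit | 3.4.1 item 4 | Yes, with consent |
| Muscle pain with CK above 1000 U/L | 3.4.1 item 5 | Yes, with consent |
| Asymptomatic liver enzymes below 3 times the upper limit | 3.2.2: repeat the test, reverse a recent dose increase if worse | Remains in the trial |
| Another abnormality, possibly drug related, in a patient able to continue | 3.4.2 | None provided |

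An example of the last row is myalgia with CK at or below 1000 U/L in a patient who could carry on. Item 5 is not met, and 3.2.2 deals with laboratory values. Section 8.1 lists "Muscle discomfort or myalgias without significant (>3 x ULN) elevations of CK" as expected and not reportable, but that is a reporting rule and does not say the patient stays in. On its words alone, 3.4.2 applies. Nothing elsewhere in the protocol restores scans after off-study removal.

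**2. What is lost.** A patient removed before month 12 has no post-baseline carotid MRI. One removed between months 12 and 24 has one, which the mixed model still uses.

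**3. Planned power reproduced.** Inputs from 6.0: baseline mean 300 mm3, decreases of 40% and 20%, SD of change 125 mm3, 80 per arm, 5% level (two-sided is assumed here, and it reproduces the table).

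- Difference: (0.40 − 0.20) × 300 = 60 mm3.
- Noncentrality: 60 / (125 × √(1/80 + 1/80)) = 3.036 on 158 degrees of freedom.
- Power by noncentral t: 0.855, against 0.85 in the table.
- Recruitment: 160 / (1 − 0.20) = 200, as stated.

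**4. Extra losses from one arm.** With 80 vs 79, power is 0.853. With 80 vs 78, it is 0.850.

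**5. Possible shift in an arm mean.** The documents give neither the number of removals nor how those patients' wall volumes would have changed. Assume that each removed patient's unseen 24-month change differs from the value the model implies by up to D = 125 mm3, one SD of change. With k removals, all in one arm of 100 randomized, the largest shift is (k/100) × D.

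| k | Largest shift (mm3) | Share of 60 mm3 |
|---|---|---|
| 1 | 1.25 | 2.1% |
| 2 | 2.5 | 4.2% |
| 5 | 6.25 | 10.4% |

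The shift can go either way.

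**6. The one related frequency.** The CK row in 5.3 gives a discontinuation frequency below 1%, which is fewer than 0.01 × 200 = 2 patients. It does not bound other 3.4.2 abnormalities, such as myalgia with a lower CK, for which no frequency is given.

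**The case against.** The best defence is that the 3.4.2 group may be nearly empty. Item 2 of 3.4.1 covers adverse reactions with no threshold of certainty, and items 4 and 5 cover the main liver and muscle toxicities. Section 3.2.2 and the concern column of 5.3 show that milder abnormalities are meant to be watched. The mixed model uses 12-month scans, and 20% attrition is already budgeted. All of this stands, and it keeps the point small. It does not remove it: a suspected effect in a patient able to continue still meets the words of 3.4.2, and an attrition allowance protects precision, not against loss that depends on treatment.

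A reader might infer more than the documents support:

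- *That 3.4.2 forbids scans, or expels everyone with a mild statin effect.* It makes no provision for scans, which is different from a ban. The monitoring provisions suggest that wholesale removal was not intended.
- *That the result is biased in a known direction.* Both arms receive statins, and therapy in the imaging arm may be intensified or reduced.
- *That the LDL targets contradict one another.* Titrating to 40 to below 70 mg/dL meets all four statements. What is open is whether to reduce the dose when LDL is under 40, since 3.2.1 allows reduction to return to target. No frequency is given for this.
- *That the CK rules in 3.2.2 clash.* The statement that "CK >1000 U/L will be considered a serious adverse event as per section 8.1" concerns reporting, and is compatible with repeating the test or stopping the drug. The repeat-test rule covers results "ALT, AST, alkaline phosphatase, CK > 1000 U/L) that are asymptomatic and less than 3 times the upper limit of normal", and the documents give no upper limit for CK, so whether a value above 1000 U/L can qualify cannot be settled. The mismatch that remains is between 5.3 and 3.4.1 item 5.

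**Conclusion.** The point holds as a moderate design weakness, worth correcting. Read as written, 3.4.2 ends outcome measurement for a possibly treatment-related reason, while 3.4.1 preserves it for closely similar patients.

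The group is probably small, the direction of bias is unknown, and no stated power or sample size is wrong. The 2% to 10% range is illustrative. It depends on two assumptions from outside the documents: one to five removals, all in one arm, and a departure of up to 125 mm3 for each. If nobody was removed under 3.4.2, the concern has no effect on the results.

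The CK symptom mismatch and the missing rule for top-tertile LDL under 40 are secondary. Neither adds weight to the main point.

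**What to change.** **Wording.** Make the 3.4.2 abnormality sentence an off-treatment criterion under 3.4.1, with imaging and event follow-up continuing unless consent is withdrawn or imaging is unsafe. This is cheap, but it cannot recover scans already missed.

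**Now, in analysis.**

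- Report 3.4.2 removals by arm, reason and timing relative to the 12-month scan.
- If there were any, run one sensitivity analysis of the mixed model that shifts their missing 24-month wall volume over a stated range, for example −125 to +125 mm3 (an assumed range).

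The cost is a count from existing records and at most one additional analysis.

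**Minor.** Align the CK stopping rule between 5.3 and 3.4.1 item 5, and state whether the dose is reduced for top-tertile LDL under 40. The clinical choice is the sponsor's. At this stage it is enough to report how such cases were handled.
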